3.2.2 Secondary Outcome Measures

Secondary outcomes will be assessed through clinical dental screenings for new primary and permanent decayed and filled teeth (dft/DFT: number of new cavitated lesions or restorations on teeth that were previously sound and number of new restorations on teeth that were previously decayed at the baseline WCV), questionnaire responses for oral hygiene (frequency of tooth brushing), diet (frequency of sweet food and drinks), and oral health-related quality of life (ECOHIS, numeric score) (Pahel et al., 2007). The direct and indirect dental costs will be assessed through various sources (See Table 8.1.2 for more details on cost elements and sources).

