8.1.1 Child-level

The primary (i.e. dental attendance) and secondary outcomes (i.e. new decay, oral hygiene, frequency of sweet food and drinks, oral health-related quality of life, and dental-related costs) are also implementation measures of effectiveness. Child medical illness is a confounder.

Child dental attendance (i.e. receipt of dental care) will be assessed through:

- Clinical dental screenings will be performed at all 3 WCVs (T_0 , T_3 , and T_6) by a trained and calibrated dental hygienist according to the International Caries Detection and Assessment System (ICDAS). The screenings will be used to identify a change in oral health status between WCVs #1 and #2 (T_0 and T_3) and WCVs #2 and #3 (T_3 and T_6) which is defined as a restoration (ICDAS ≥ 3) or extraction of ≥ 1 tooth previously identified with an active ICDAS lesion code ≥ 3 at T_0 or T_3 that would not be exfoliated naturally based on child's age. See ICDAS Assessment form (Appendix E). More details on the screening and decision algorithm will be outlined in the MOP Section 5.
- B2: Dental Attendance & Cost Questionnaire: Study staff will contact caregivers 6 months after WCVs #1 and #2 (T_1 and T_4) to ask whether their child had a dental visit or if they made a dental appointment for their child since the previous WCV (Appendix E).
- Medicaid claims files: Data will be abstracted by study staff to verify child's receipt of dental care after each WCV (T_1 , T_4 , and T_7) and entered on the Medicaid Claims Abstraction form. Current Dental Terminology (CDT) codes used for billing will be used to determine if the child received preventive or restorative procedures in the past 12 months. Dental emergency department (ED) visits will be identified by linking diagnosis codes (Appendix E) to ED claims using the International Classification of Diseases, Tenth Revision, Clinical Modification (ICD-10-CM). See Medicaid Claims Abstraction form (Appendix E) for preventive and restorative CDT codes and ICD-10-CM codes.
- COVID-19 Questionnaire: At WCV3, actively enrolled parent/caregivers will complete a short (7 item) COVID-19 Questionnaire which asks if they have altered their behavior related to taking their child to the dentist due to the COVID-19 pandemic.

Secondary outcomes and child medical illness (i.e. confounder) will be assessed as follows:

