- A newly carious tooth is defined as any tooth receiving an ICDAS lesion code ≥ 3 that received a sound code on the previous dental screening or any tooth surface with an ICDAS filling code ≥ 3 that previously did not have one. Number of teeth with new decay or filling will be assessed through the clinical dental screenings (T_0 , T_3 , and T_6) and recorded on the ICDAS Assessment form (Appendix E).
- Questions on frequency of tooth brushing (NHANES III)(CDC), frequency of consumption of sweet food and drinks (NHANES 2009-2010; Youth Risk Behavior Survey 2017)(CDC, 2017; CDC, 2014), and the 13-item Early Childhood Oral Health Impact Scale (ECOHIS)(Pahel et al., 2007) will be used to measure oral hygiene, frequency of sweet food and drinks, and oral health-related quality of life (OHRQoL), respectively. Higher scores on

the ECOHIS indicate poorer OHRQoL. These questions are included on the A2: Parent Questionnaire (Appendix E) which will be completed at all 3 WCVs (T_0 , T_3 , and T_6).

- Direct dental costs include costs of preventive and restorative procedures, and dentalrelated ED visits. These costs will be abstracted from Medicaid claims files as part of the verification of child's dental care receipt (described above) and recorded on the Medicaid Claims Abstraction form. Non-dental direct costs (transportation) and dental indirect costs (time away from work, household, or leisure activities) are measured using questions adapted from the Annotated Cost Questionnaire (Thompson & Wordsworth, 2001) which are incorporated into the B2 Follow-up Questionnaire. The B2 Questionnaire will be administered after WCVs #1 and #2 (T_1 and T_4). Study staff will administer the cost questionnaire at WCV #3 (T_6) to identify any lags in receipt of dental care. Cost data from Medicaid claims files will be abstracted at 3 time points (T_1 , T_4 , and T_7). See the Annotated Cost Questionnaire and Medicaid Claims Abstraction form (Appendix E) for more details.

Table 8.1.2 Cost elements and sources

Cost Category	Cost Element	Source
Implementation/ training costs	Training providers in communicating oral health facts	Study training records/logs
	IT system modifications	Vendor invoices, clinic personnel time logs
	Staff training	Study staff time/training logs
Intervention costs	Time required to provide education and give prescription	Review of audiotaped encounters
	Cost of dental prescription pads, flip charts, pocket cards	Study/practice expense records

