The primary objective is to compare dental care attendance between the two arms. For simplicity in the power calculation we consider the binary outcome of any dental attendance in the two year period of follow-up. Dental attendance will be based on a single summary score (number of years - out of two - in which the child visits the dentist at least once a year). We thus suppose the use of a two-sided 0.05 alpha level z test (with pooled variance) for a difference in proportions. We assume, as a rough approximation, that the study will recruit an equal number of patients in each practice. Making conservative allowances for an intra-cluster (within-practice) correlation (ICC: in the binary dental attendance outcome) of 0.04 and a 25% drop-out rate, a sample size of 512 participants per arm (total n= 1024) will provide an estimated 80% power to detect the above difference in proportions. Alternatively, this sample size (actually 438 per group) will provide 90% power to detect this same effect size if the ICC is only 0.02. If the intervention effect is only 0.12 (0.42 versus 0.30), a sample size of 457 per group (914 total) will still provide 80% power with a dropout rate of 25% if the ICC is only 0.01. For the purposes of this study, a sample size of 512/arm (n=1024) will be recruited.

For sample size estimates, an important secondary outcome will be incidence of new decayed or filled teeth (dft). Mean dft is hypothesized to decrease for Arm A relative to Arm B. Our

previous data (Lee et al. 2015) among 5 to 7 year old low-income children suggests a mean dft for usual care of 4.5 (standard deviation = 7) which we assume to be a reasonable value for the enhanced usual care arm in the present study. We assume the same standard deviation for the new intervention group, assuming normally distributed responses for the power calculation. In fact, as dft is a count (possibly following a distribution such as Poisson or negative binomial) it is likely that the standard deviation will decrease with the mean, making our approach conservative (McCullagh and Nelder 1989).

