will be modified by using a linear model (identify link) for GEE, modeling the mean response over time as a summary measure. These outcomes will each be tested for normality using the Shapiro-Wilk statistic; outcomes for which normality is violated will be transformed where appropriate or an alternative model used. For count outcomes (e.g., dft accumulated over time), we will use a loglinear model (log link) assuming a negative binomial or other appropriate (e.g., zero-inflated negative binomial) distribution. For proportion outcomes (e.g., dt/dft), we will use GEE with a logit link, assuming the proportion follows a beta binomial or zero-inflated beta binomial distribution (Albert et al 2014). Similarly, we will fit appropriate GEE models to test for the effect of each implementation strategy on the corresponding outcome (e.g., % prescriptions given as a measure of adoption). As in the dental attendance analysis, the intervention indicator as well as pertinent baseline variables will be included in the model. In addition, interaction terms (baseline variables by intervention) will be included to test for possible effect modification.

For secondary analyses, a GLIMMIX model approach will be considered as an alternative, which may more easily allow for more than one cluster level if needed. Another alternative approach is to model the repeated measurements (again using GEE or GLIMMIX) which will add an additional cluster level – namely, for individuals). Goodness of fit of alternative models will be compared using QIC for GEE (or AIC for GLIMMIX).

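### The new-caries count treats the filling of an already decayed tooth as new disease, which would dilute a preventive effect if Arm A receives more restorative care

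*Combined protocol and SAP*

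**What the plan says.** Section 3.2.2 puts two components under new dft/DFT: new lesions or restorations on teeth that had been sound, and the "number of new restorations on teeth that were previously decayed at the baseline WCV".

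Section 8.1.1 gives the working definition of a newly carious tooth. Its lesion limb requires a sound code at the previous screening. Its filling limb does not: it accepts "any tooth surface with an ICDAS filling code ≥ 3 that previously did not have one". A single figure is then recorded: "Number of teeth with new decay or filling will be assessed through the clinical dental screenings".

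The same section uses the screenings as evidence of dental attendance, through a restoration or "extraction of ≥ 1 tooth previously identified with an active ICDAS lesion code ≥ 3".

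The other places that bear on the count do not agree with one another:

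- Table 8.1.1 scores the outcome simply as decayed and filled teeth.
- Section 12.2 says that "an important secondary outcome will be incidence of new decayed or filled teeth (dft") and expects mean dft to be lower in Arm A.
- Section 12.4 models dft accumulated over time with a log link, and adds a proportion analysis: "For proportion outcomes (e.g., dt/dft), we will use GEE with a logit link".

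**The concern.** Secondary objective 1 (section 3.1) names the development of new caries. A count that rises when existing decay is treated does not measure that. The direction is awkward for this trial, because the intervention aims to bring children to the dentist and section 4 says it addresses untreated caries. One filling can thus be a success on attendance and a failure on caries.

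If Arm A raises restorative care, its count goes up for a reason unrelated to prevention, and a null caries result could not be read as absence of a preventive effect.

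There is also a problem of reproducibility. Section 3.2.2 refers to teeth and to baseline. Section 8.1.1 refers to the previous screening in one limb and to surfaces in the other. Neither says that a tooth counts only once. Two analysts could follow the plan and produce different endpoints.

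**Working it through.** **Tooth histories.** Take the three screenings at T0, T3 and T6, with S sound, D decayed (lesion code 3 or above) and F filled. The second column applies section 8.1.1 to each interval and sums the two intervals. The third counts teeth sound at T0 that later show a lesion or filling, once each. The fourth is the change in ordinary dft from T0 to T6.

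| History | 8.1.1, intervals summed | Sound at T0, once per tooth | Change in dft |
|---|---|---|---|
| D-D-D | 0 | 0 | 0 |
| D-F-F | 1 | 0 | 0 |
| D-D-F | 1 | 0 | 0 |
| S-D-D | 1 | 1 | 1 |
| S-D-F | 2 | 1 | 1 |
| S-F-F | 1 | 1 | 1 |

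The 8.1.1 count departs from the other two only where a decayed tooth is later filled. The double count for S-D-F arises only if interval counts are summed. The dt/dft proportion in section 12.4 separates decayed from filled teeth but not new disease from old, so it does not resolve the problem.

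**The plan's own power figure.** Section 12.2 gives 74% power for mean dft of 4.5 versus 2.7, SD 7, 512 per arm, 25% dropout and an ICC of 0.02.

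- Completers per arm: 512 × 0.75 = 384; per practice 384/9 = 42.7.
- Design effect: 1 + (42.7 − 1) × 0.02 = 1.833; effective n = 384/1.833 = 209.5 per arm.
- Standard error: 7 × √(2/209.5) = 0.684; 1.8/0.684 = 2.63; 2.63 − 1.96 = 0.67, giving power of 74.9%.

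The figure reproduces. It cannot be used to express the artefact as lost power, because 4.5 (SD 7) is a cross-sectional mean dft in children aged 5 to 7. The documents give no mean or SD for two-year incidence.

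**Size of the artefact (illustrative).**

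- From the documents: 36% of pilot children (31 of 86) had untreated cavitation (section 2.2); planned attendance is 0.46 versus 0.30, a gap of 0.16 (section 12.2).
- Assumed, not in the documents: 2 to 4 decayed teeth per affected child; 50% to 100% of them filled among attenders; a share of the gap (0, one half or all) that applies to children with decay.

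Excess count per child in Arm A = share of gap × 0.16 × 0.36 × decayed teeth × proportion filled.

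| Share of gap | Low (2 teeth, 50%) | High (4 teeth, 100%) |
|---|---|---|
| 0 | 0 | 0 |
| 0.5 | 0.0288 | 0.1152 |
| 1 | 0.0576 | 0.2304 |

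**Extraction offset.** The count has no missing-tooth component, so a tooth that decays and is extracted between screenings drops out of it. More attendance could remove such teeth from Arm A's count. With the whole gap applying, the artefact per extra attender is 0.0576/0.16 = 0.36 to 0.2304/0.16 = 1.44 teeth. Extractions cancel it only if each extra attender has, on average, that many newly decayed teeth extracted between screenings.

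**The case against.** The strongest reply is that the analysed variable may not be the one in section 8.1.1. Section 3.2.2 joins two counts without saying they are added; kept apart, they come close to the split proposed here. Table 8.1.1 scores plain dft, section 12.2 powers on mean dft, and section 12.4 refers to accumulated dft. With ordinary dft the artefact disappears. This stands as a real ambiguity, but it does not clear the plan: section 8.1.1 merges the two kinds of event into one number, section 12.2 speaks of incidence, and no section specifies an analysis restricted to teeth that were sound.

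Double counting is conditional. No section says that interval counts are summed, and section 3.2.2 limits its second component to teeth decayed at baseline, so it would not add a second count for a sound-decayed-filled tooth. The detailed caries assessment is deferred to the manual of procedures, and the longitudinal coding to the coordinating center; either may contain a rule that is not visible here. That also stands, although the protocol's own definition should not depend on it.

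The size is uncertain. Teeth per child and proportion filled are assumptions. The 30% is parent-reported routine visits, and attendance includes preventive care. Section 2.1 says caregivers respond to pain or visible decay, and section 7.2.1 lets urgent screening findings reach providers in both arms, so restorative care may not differ. This is why the range starts at zero.

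Finally, the bias hides benefit rather than creating it, and it concerns one secondary outcome. This limits the importance of the point but does not remove it.

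**Conclusion.** The concern holds. Read literally, sections 3.2.2 and 8.1.1 score treated old decay as new caries and untreated old decay as zero. The wording is clear; what is uncertain is whether this count reaches the analysis and how large the effect would be. On the stated assumptions the artefact is 0 to 0.23 tooth per child, towards or past the null, and it exists only if Arm A has more restorative care and ordinary dft is not what is analysed. Extractions may offset part of it. No loss of power is claimed. The definition should be corrected because it affects a named secondary objective that section 12.2 calls important.

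**What to change.** In sections 3.2.2 and 8.1.1, define the new-caries count as the number of teeth sound at WCV #1 that later show an ICDAS lesion code of 3 or above or a filling, each tooth counted once. Keep the plan's own criterion for sound, and treat teeth unerupted at WCV #1 as sound. State how a tooth that is sound at one screening and extracted before the next is handled. Name this count in section 12.4 as the variable for the log-link model. Report restorations of teeth decayed at baseline as a separate outcome, treatment of existing decay, so that information is kept.

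Optional additions:

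- A sentence in section 12.2 saying that 4.5 (SD 7) is a cross-sectional mean dft used as a proxy for the incidence count.
- A sensitivity analysis at surface level.
- A sensitivity analysis in which every tooth below ICDAS 3 at baseline is at risk.

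The cost is wording and programming, since ICDAS is recorded at T0, T3 and T6. No new sample size calculation is needed. Because this is Version 9.0, the change should be justified, dated and made before database lock.

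The downsides are fewer counted events, and a main count that omits new lesions on other surfaces of baseline-decayed teeth and progression from ICDAS 1–2. The two sensitivity analyses cover these omissions, and the surface-level one needs a rule for fillings that span old and new surfaces. A filling placed on a sound tooth for a lesion below ICDAS 3 would still count as new. That residual bias is not quantified.

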3.2.3 Mediators, Moderators, Confounders, & Implementation Measures

Mediators, moderators, confounders, and implementation measures will be assessed at the parent, provider and practice levels. The interventions are likely to influence mediators at the practice level (EMR documentation and practice readiness, climate, attitude) and at the provider level (oral health knowledge and self-efficacy). Subsequently, providers improved oral health knowledge and communication of oral health facts to parent is likely to influence parent-level mediators (illness perception and parent self-efficacy to take the child to the dentist). The moderators for the relationship between the interventions and the primary/secondary outcomes are parental socio-demographics, health literacy and social support and the confounders are child medical illness. Provider socio-demographics can also be a moderator to this relationship. See Sections 4 (Figure 4.2.1) for more details on mediators, moderators and confounders and Table 8.1.1 for implementation measures and for more details regarding how these measures will influence the primary and secondary outcomes.

3.3 Additional Objective with Supplement

To evaluate the process and outcomes data from the implementation of the cluster randomized clinical trial, together with additional provider qualitative data on barriers/enablers (using Roger's Diffusion of Innovation framework) collected during this revision for the development of a toolkit for dissemination to stakeholders.

As part of the supplement, providers will complete a follow-up structured interview and debriefing session.

4 STUDY DESIGN

This study will utilize a multi-site, multi-level, and multi-component cluster randomized clinical trial design (Phase III) to assess interventions intended to address poor dental utilization (attendance) and untreated caries among 3-6 year old Medicaid-enrolled children attending well-child visits (WCV) in primary care settings. The focus is on addressing factors (determinants) at the socio-ecological levels of the child's environment: provider (pediatrician and nurse practitioner), parent/caregiver and practice/organization levels. Eighteen practices will be randomized to 2 arms for provider training and practice/organization level study intervention changes: A) provider-level CSM training, provision of oral health facts to parents, a prescription and a list of dentists accepting Medicaid + practice-level EMR changes for documenting oral health; B) AAP training with no prescription or list of dentists accepting Medicaid and no changes to the EMR. Arm A parents/caregivers will receive oral health facts and prescription to take their child to the dentist and improve oral health behaviors in the home, while Arm B parent/caregivers will receive usual AAP-based care for oral health. Each arm will consist of 9 practices (n= 18), 33 to 34 providers (n= 67), and 512 parent/caregiver and child dyads (n= 1024). Each parent/caregiver and child dyads will be recruited at the first WCV and then followed for two consecutive WCVs (for a 24 month duration or until the subject has completed 3 well child visits). Each provider will complete the didactic and skills training prior to enrolling any parent/caregiver and will participate in the study for a total of 24 months duration (includes initial and booster didactic and skills training: 3 months, WCV#1: 3 months, WCV#2: 3 months, WCV#3: 3 months). Data will be collected prior to WCVs, at WCVs, and follow-up visits.

Immediately after randomization of practices, recruitment will be rolled-out, i.e. parent/caregivers will be recruited during a 3-month period in 6 practices at a time, with recruitment at all 18 practices expected to be completed in 9 months. This strategy will maximize staff time and ensure that EMR integration of OH is complete at practices randomized to Arm A, and that providers receive the didactic and skills training prior to their practice's rollout.

4.1 Study participants

Subjects will be pediatric providers (Pediatricians/Nurse Practitioners) and parent/caregivers and their 3-6 year old children from 18 primary care practices located in Ashtabula, Cuyahoga, Geauga, Lorain, Medina, and Portage counties in Ohio (see Table 4.1.1 below). One additional practice not included in the table, Premier Pediatrics, has also agreed to participate and will be included if needed to replace a practice. The majority of the practices are in Cuyahoga County (67%) and the remaining 33% are in surrounding counties in NE Ohio. All practices serve $\geq 20\%$ Medicaid eligible children (9 practices with 20-40% and 9 practices with $> 40\%$ Medicaid-eligible children) and are from the Rainbow Care Connection (RCC). The study is offered to all pediatricians/nurse practitioners in the recruited practices and will be offered to all eligible caregivers and their children excluding those with serious medical or behavioral conditions which would preclude them from participating in the dental screening. All provider and parent participants meeting the eligibility criteria will be enrolled in the study upon signing the consent form.

Table 4.1.1 Practice Information

Practice/Site	# Pediatricians	# Nurse Practitioners	Medicaid Patients (age 3-6)	Medicaid Patients w/WCV (age 3-6)	% Medicaid	County
Ashtabula Pediatrics	1	2	592	448	63%	Ashtabula
Chardon Pediatrics	4	1	387	267	34%	Geauga
Elyria Pediatric Care	3	0	205	168	33%	Lorain
Healthy Kids Pediatrics	1	1	121	95	31%	Portage
[name]	1	0	344	340	80%	Cuyahoga
Medina Pediatrics	4	2	338	250	23%	Medina
NEON	5	0	1856	357	80%	Cuyahoga
Otis Moss	2	0	297	233	82%	Cuyahoga
Pediatric and Adolescent Health Professionals	3	0	157	118	22%	Cuyahoga
Pediatric Partners of Cleveland	2	0	209	165	40%	Cuyahoga
Pediatric Services - Parma	8	0	740	588	30%	Cuyahoga
Pediatriccenter – Garfield	2	0	561	384	24%	Cuyahoga
Rainbow Ambulatory Clinic	4	0	2728	2361	86%	Cuyahoga
Rainbow Euclid Pediatrics	1	0	246	186	68%	Cuyahoga
Suburban Pediatrics - Shaker	7	0	408	335	23%	Cuyahoga
University Premier Pediatricians – Euclid	4	1	504	418	49%	Cuyahoga
UH Westshore Primary Care **	4	0	424	185	45%	Cuyahoga
University Pediatrics of Lorain	4	0	653	523	61%	Lorain
Totals	60	7	10,302	7,421		

Practice information data captured 1/1/2016 through 12/31/2016.

**Data captured 1/1/2017 through 5/31/2017

